9.7.2.2 Analysis of LV Opacification

The proportion and its 95% CI of subjects with adequate LV opacification scores at the CEUS will be estimated using binomial proportion estimate method. Assuming expected proportion of subjects with adequate LV opacification scores at the CEUS is 80%. The success criteria for the LV opacification score will be 2 out of 3 blinded readers reach >70% as the lower limit of 95% confidence limit for the proportion of subjects with adequate LV opacification score.

Inter-reader agreement of the assessment of adequate LV opacification for each subject among 3 off-site readers will be evaluated by kappa statistic.

9.8 Sample Size

Sample size determination for this study was based on the 2-tailed paired t-test using software nQuery Advisor 7.0. The primary objective of this trial is to show a significant intra-subject change in total of LV EBD scores for each subject (Hypothesis specified above) from UEUS to LUMASON -enhanced echocardiography. Sample size determination for this study was based on the 2-tailed paired t-test.

A peer-reviewed publication showed ³⁷ that the percentage of endocardial border visualization at unenhanced harmonic images (74%) was significantly lower comparing to a contrast enhanced images (88%) in the suboptimal subjects non-diagnostic imaging group, which translated to the difference of 4 in total LV EBD scores. A previously conducted Bracco-sponsored study [REDACTED] had the same endpoint of the total LV EBD score range 0-32 assessed on harmonic

images on adult subjects with known or suspected coronary artery disease. The results from the analysis of the suboptimal subjects in this study showed that the average difference of the total LV EBD score between CEUS and UEUS was 3.2; the standard deviation of the difference was 8.3. Based on these results as the assumptions for current study and considering the probability of a Type I error (α) of 0.05 and the probability of a Type II error (β) of 0.10, 73 subjects will be needed to show a difference between CEUS and UEUS for 90% of power.

When the sample size is 73, a 2-sided 95% CI for a single proportion using the large sample normal approximation will extend 9% from the observed proportion for an expected proportion of 80% subjects with adequate LV opacification score. This can be translated as lower limit of 95% CI >70% for the observed proportion of subjects with adequate LV opacification score.

Based on the above considerations, for both endpoints (Total LV EBD score and LV opacification score), total of 73 evaluable subjects are needed. Considering 20% of early dropout, 92 subjects will need to be enrolled.

A subset of 12 subjects is considered to be sufficient for the estimation of the pharmacokinetic parameters, based on the findings of a prior study in healthy subjects.

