9.7 Efficacy Analysis

The primary analysis will be based on the off-site reader evaluations. The analysis will be performed and presented separately for each reader. There will be no adjustment for multiple readers. There will be 2 primary endpoints for the study: the change from baseline (UEUS to CEUS) in total LV EBD score and proportion of subjects with adequate LV opacification. As we have to achieve success for both endpoints there will be no multiplicity adjustment for the analysis and power consideration.

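### Section 9.8 supports 73 subjects for the required LV opacification co-primary by interval width alone; at the plan's own 80% and named interval, a reader meets the success rule only 61% of the time

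*Combined protocol and SAP*

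**What the plan says.** Section 9.7 names two primary endpoints, the change in total LV EBD score and the proportion of subjects with adequate LV opacification, and requires both: "As we have to achieve success for both endpoints there will be no multiplicity adjustment for the analysis and power consideration".

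Section 9.7.2.2 takes 80% as the expected proportion with adequate opacification. The endpoint is met if "2 out of 3 blinded readers reach >70% as the lower limit of 95% confidence limit". On the interval, it says only that the proportion and its 95% CI "will be estimated using binomial proportion estimate method".

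Section 9.8 gives a power for the EBD paired t-test: "73 subjects will be needed to show a difference between CEUS and UEUS for 90% of power". For opacification it says that, with 73 subjects and an expected 80%, a two-sided 95% interval "using the large sample normal approximation will extend 9% from the observed proportion", and adds: "This can be translated as lower limit of 95% CI >70% for the observed proportion of subjects with adequate LV opacification score". It concludes that "for both endpoints (Total LV EBD score and LV opacification score), total of 73 evaluable subjects are needed". No power or probability of success for opacification appears anywhere in the document.

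**The concern.** A half-width describes the interval once a particular proportion has been observed. It does not say how often the trial will observe a proportion high enough to pass. Section 9.8 moves from one to the other: because an observed 80% has a lower limit just above 70%, it treats 73 subjects as enough for the endpoint. If 80% is the true rate, the observed rate falls above or below it with sampling error, and a pass mark close to 80% will be missed in a large share of trials.

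Since both co-primaries must succeed, the weaker one limits the whole study. A reader of section 9.8 who takes 90% as the power of the trial would be misled about its chance of meeting the primary objective.

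**Working it through.** **Inputs.** From section 9.8: n = 73 evaluable; EBD mean difference 3.2, SD of the difference 8.3, two-sided α = 0.05, power 90%; two-sided 95% CI by the large-sample normal approximation; dropout 20%. From section 9.7.2.2: expected proportion 80%; lower 95% limit above 70% for two of three readers.

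**1. The plan's own figures reproduce.**
- EBD paired t-test: noncentrality (3.2/8.3)·√73 = 3.29, power 90.1% (72 subjects give 89.7%).
- Half-width: 1.96·√(0.8·0.2/73) = 0.0918, so the lower limit at an observed 80% is 0.80 − 0.0918 = 0.708.
- Enrolment: 73/0.8 = 91.25, rounded up to 92.

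**2. Pass mark for one reader.** Find the smallest count r with r/73 − 1.96·√[(r/73)(1 − r/73)/73] > 0.70.
- r = 57: 0.7808 − 1.96·0.0484 = 0.686, fails.
- r = 58: 0.7945 − 1.96·0.0473 = 0.702, passes.

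The expected count at a true 80% is 73·0.80 = 58.4.

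**3. Probability that one reader passes**, with X ~ Binomial(73, 0.80): P(X ≥ 58) = **0.614**.

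**4. Two-of-three rule**, all readers at 80%, with q = 0.614.
- Perfect agreement: 0.614.
- Independent readers: 3q²(1 − q) + q³ = 0.668.
- Simulated readers with equal rates and intermediate correlation fall between these: 0.648 at kappa 0.23 and 0.631 at kappa 0.56.

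**5. Both co-primaries, one reader**, whatever the dependence between endpoints.
- Lower bound: 0.614 + 0.9015 − 1 = 0.516.
- Upper bound: min(0.614, 0.9015) = 0.614.

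**6. Sensitivity to the interval**, since section 9.7.2.2 does not name one. The last column solves P(X ≥ r) = 0.90 for the true rate.

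| Interval | Pass mark (lower limit) | One below (lower limit) | P(pass) at 80% | True rate for 90% |
|---|---|---|---|---|
| Normal approximation | 58 (0.702) | 57 (0.686) | 61.4% | 84.3% |
| Wilson | 59 (0.703) | 58 (0.688) | 50.0% | 85.5% |
| Exact (Clopper-Pearson) | 60 (0.715) | 59 (0.699) | 38.4% | 86.7% |

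**7. Sensitivity to the true rate**, normal approximation, one reader: 44.8% at a true 78%, 61.4% at 80%, 76.9% at 82%, 92.7% at 85%.

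**The case against.** The strongest reply is that no printed number is wrong. Section 9.8 says twice that the size was based on the paired t-test, attaches 90% to that test alone, and describes opacification openly in terms of interval width. On this reading, the conclusion about both endpoints means power for one and precision for the other. It is true that the half-width is correct and that no opacification power is claimed. But precision is not a sufficient basis for an endpoint with a fixed pass mark that the study must meet, and the document gives no other basis.

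A second reply is that section 9.7 declares that power will not be adjusted. It does, but the reason given does not carry over. Requiring both endpoints removes the need to adjust the type I error; it lowers power.

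A third is that 80% may be conservative, and success rises quickly above it. The plan gives no source for 80% and presents it as the expected value. If a higher rate is expected, section 9.8 should say so.

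A fourth is that the reported ranges depend on reader agreement, equal reader rates and the interval, none of which the plan fixes. That stands, and the figures are conditional on it. The named normal approximation is also the most favourable of the intervals tried. Fewer dropouts would not help: if all 92 enrolled were evaluable, the per-reader figure at 80% would be 62.2%.

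Finally, a wording change leaves the chance of success as it is. That is so. What it corrects is a justification that does not support its conclusion.

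**Conclusion.** The concern holds. On the plan's own inputs (73 evaluable subjects, a true rate of 80%, the normal-approximation interval), each reader meets the opacification rule with probability 61.4%. With equal reader rates, and dependence anywhere from full agreement to independence, the two-of-three rule gives 61.4% to 66.8%. The criterion is therefore missed about 33% to 39% of the time when the product performs exactly as assumed. Overall power cannot exceed the study-level opacification figure, so the 90% quoted for EBD is not the power of the trial. Wilson or exact limits would lower the per-reader figure to 50.0% or 38.4%. The conclusion is tied to the stated 80%: with 73 subjects, 90% per-reader power requires a true rate of 84.3% under the named interval.

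**What to change.** In section 9.8:
1. Label the half-width sentence as precision only, and remove or qualify the statement that 73 subjects are what both endpoints need.
2. Name the interval that will be used, consistently with section 9.7.2.2, and state the probability of meeting the rule at a true 80%: 61.4% per reader for the normal approximation, 50.0% for Wilson or 38.4% for exact. Only the figure for the chosen interval is needed.
3. State the true rate at which 73 subjects give 90% per-reader power: 84.3%, 85.5% or 86.7% respectively.
4. State that overall power is bounded above by the opacification power.

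In section 9.7, limit the no-adjustment statement to type I error and say that requiring both endpoints lowers power. Because the sentence now names power expressly, this corrects the text rather than clarifying it.

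The cost is wording in sections 9.7 and 9.8, plus naming one interval. The stated probability of success becomes less favourable. No extra subjects, procedures or changes to the success rules are requested.

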9.9 Data Handling

All data collected will be entered into the database and displayed in the data listings and tables. Detail of the data handling procedures will be specified in the SAP. Baseline values will be defined as the last measurement prior to administration of the IP.

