7.1 Study Schedule

Table B: Study Schedule

	Pre dose			Post dose				
	Within -24 h	Within -30 min ^e	Prior to IP administration	0 min	5 min	30 min	24 h	72 h
Written Informed Consent^a	×							
Adverse Events Monitoring^b	×	⇒	⇒	⇒	⇒	⇒	⇒	×
Concomitant Medications^c	×	⇒	⇒	⇒	⇒	⇒	×	× ^f
Medical History	×							
Physical Examination	×						×	
Vital Signs		×			×	×	×	
Pregnancy Test (if necessary)	×							
Pulse Oximetry/ ECG monitoring^d		×	⇒	⇒	⇒	×		
Laboratory Evaluations	×						×	
12-Lead Electrocardiogram		×				×	×	
IP Administration				×				
Unenhanced Echo			×					
Contrast Enhanced Echo				×				

a Obtain prior to implementation of any study procedure.

b Start monitoring from the time Informed Consent is given up to 24 h post dose and continue monitoring up to 72 hrs post dose through a telephone call placed at Day 3. Only post dose events will be tabulated as adverse events.

c For any subject where sedation is administered, record the sedation medication on the concomitant page of the CRF and indicate for sedation.

d Continuous pulse oximetry and ECG monitoring will be performed 30 min prior through 30 minutes following IP administration for all subjects suffering from pulmonary hypertension or unstable cardiopulmonary conditions.

e For any subject where sedation is administered, obtain a second vital sign series and ECG immediately before the echocardiography exam and after the sedation drugs have been administered.

f Record any new medication taken for treatment of an adverse event that occurred after the signed informed consent was obtained through 72 hours following IP administration.

Note: A subset of 12 subjects will undergo additional blood draws for analysis of SF₆ concentrations, (see Section 7.6).

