7.4.4.3 Vital Signs

Collect the following vital signs within 30 minutes pre dose and at 5 minutes, 30 minutes and 24 hours post dose. Obtain the following vital signs in a position that is consistent for all time points for each subject:

- Systolic blood pressure (mmHg)
- Diastolic blood pressure (mmHg)
- Heart rate (beats/minute)
- Respiratory rate (breaths/min)

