7.4.4.5 Electrocardiograms

A 12-Lead Electrocardiogram (ECG) will be performed in all subjects within 30 minutes prior to IP administration, and at 30 minutes and 24 hours after IP administration and a copy of the ECG report will be affixed to the CRF.

The ECG examinations will be evaluated by a central ECG laboratory that will provide the ECG equipment to the site and will employ a cardiologist to perform the centralized ECG evaluation containing the following information:

- RR interval
- PR interval
- QRS interval
- QT and QTc interval (Bazett's and Fridericia's)
- Overall diagnostic assessment
- Comparison to Baseline

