7.4.4.7 Sedation

When children are unable to cooperate, sedation may become necessary to ensure that images of diagnostic quality are obtained. Whether or not sedation is necessary depends on several variables, including age and maturity of the subject, prior sedation history, duration of the procedure, and any associated discomfort. Subjects will be sedated or anesthetized only for

procedural purposes and then according to standard hospital routines by qualified individuals (e.g., nurses, physicians, or physician assistants) who are experienced in the management of sedated children and have the knowledge to perform careful subject screening so as not to put any subject at unacceptable risk of serious complications.

All drugs administered for sedation will be recorded on the Case Report Form on the Concomitant Medications page. Monitoring of the subject will start with documentation of pre-sedation vital signs, and ECG recordings on the Case Report Form. Continuous subject monitoring should be conducted according to routine clinical practice. When sedation is required, additional vital signs and ECG data will be performed after sedation and before the echocardiography examination and recorded on the CRF.

Whenever adverse events are recorded, the Investigators will be asked to prospectively report in the CRF their causality assessment including an evaluation of whether the event may be related to the sedation drug(s) or the IP.

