9.5 Safety Analysis

The safety data will be summarized for all subjects dosed. Summary tables, including change from UEUS to CEUS or clinically significant changes where applicable, will be presented for the following safety endpoints:

- Adverse Events
- Clinical Laboratory Evaluations
- Electrocardiograms
- Pulse Oximetry
- Vital Signs

All adverse events will be coded by MedDRA and summarized by system organ class and preferred term, by intensity and by causal relationship to the investigational product.

Only those occurrences which occur from the start of IP administration through the follow-up period defined in the protocol will be tabulated in the Clinical Trial Report as “adverse events” See Section 8.1.1.

Physical examination results, concomitant medication data will be presented in the data listings.

Summary statistics will be presented for volume of investigational product administered.

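### For sedated subjects the single baseline rule makes the post-sedation reading the baseline, so the 24-hour vital-sign and ECG changes mix recovery from sedation with any product effect (minor)

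*Combined protocol and SAP*

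**What the plan says.** Section 9.9 (Data Handling) gives one definition for all variables and time points: "Baseline values will be defined as the last measurement prior to administration of the IP". It makes no exception for sedation. The sentence before it leaves data-handling detail to the SAP; no SAP text on deriving baseline appears in the document supplied.

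Sedated subjects have two pre-dose series:

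- Section 7.4.4.7 (Sedation), first series: "Monitoring of the subject will start with documentation of pre-sedation vital signs, and ECG recordings on the Case Report Form".
- Section 7.4.4.7, second series: "additional vital signs and ECG data will be performed after sedation and before the echocardiography examination and recorded on the CRF".
- Section 7.1, Table B, footnote e, on the timing of the second series: "obtain a second vital sign series and ECG immediately before the echocardiography exam and after the sedation drugs have been administered".

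The post-dose schedule is in section 7.4.4.3 for vital signs ("Collect the following vital signs within 30 minutes pre dose and at 5 minutes, 30 minutes and 24 hours post dose") and section 7.4.4.5 for the 12-lead ECG ("within 30 minutes prior to IP administration, and at 30 minutes and 24 hours after IP administration").

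Section 9.5 describes the output: "Summary tables, including change from UEUS to CEUS or clinically significant changes where applicable, will be presented for the following safety endpoints". ECG and vital signs are both on the list that follows. Neither 9.5 nor 9.9 provides a separate baseline, flag or table for sedated subjects.

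**The concern.** A change from baseline is read as an effect of the product only if the subject is otherwise in a comparable state at both readings. For a sedated child the rule in 9.9 always picks the sedated reading. That is a fair reference shortly after dosing. At 24 hours the child has presumably recovered, so the difference contains the offset of the sedative as well as anything the product did.

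The study is open-label, non-randomized and single-arm (sections 5.1 and 6.3), so no comparison group shares the offset and cancels it. If sedation lowers the reading, a spurious rise can appear at 24 hours, or a true fall can be hidden. Obtaining safety data is a stated secondary objective (section 4), and within-subject change is the natural quantitative contrast for vital signs and ECG in this design.

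**Working it through.** The plan states no figure on this point, so there is none to reproduce. The check has two parts: which reading the rule selects, and what the resulting change contains.

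**1. Which reading is baseline.** The order of events in a sedated subject is: pre-sedation series, sedation, post-sedation series, product, then readings at 5 min (vital signs only), 30 min and 24 h. The last measurement before the product is the post-sedation series, so it is the baseline for all three post-dose times.

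**2. What each change contains.** For one sedated subject let R be the calm, unsedated level; S the amount by which sedation lowers the reading; d the amount by which distress raises the pre-sedation reading; and e the product effect at the time in question. Assume the subject is still sedated at 5 and 30 min and fully recovered at 24 h. The documents state none of these values, nor their direction.

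- Pre-sedation reading: R + d
- Post-sedation reading: R − S
- Reading at 5 or 30 min: R − S + e
- Reading at 24 h: R + e

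| Post-dose time | Change from post-sedation series | Change from pre-sedation series |
|---|---|---|
| 5 and 30 min | (R − S + e) − (R − S) = e | (R − S + e) − (R + d) = e − S − d |
| 24 h | (R + e) − (R − S) = e + S | (R + e) − (R + d) = e − d |

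The current rule recovers e at the short times but gives e + S at 24 h. The pre-sedation series gives e − d at 24 h. If S and d are both zero or positive, e lies between the two 24-hour changes.

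**3. Size in the pooled mean.** If a fraction p is sedated, the mean 24-hour change under the current rule moves by p × S. Both p and S are assumed. The counts take all 92 enrolled subjects as dosed (92 × p).

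| p (sedated, of 92) | S = 5 | S = 10 | S = 15 | S = 20 |
|---|---|---|---|---|
| 0% (0) | 0 | 0 | 0 | 0 |
| 2% (about 2) | 0.1 | 0.2 | 0.3 | 0.4 |
| 5% (about 5) | 0.25 | 0.5 | 0.75 | 1.0 |
| 10% (about 9) | 0.5 | 1.0 | 1.5 | 2.0 |
| 20% (about 18) | 1.0 | 2.0 | 3.0 | 4.0 |

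Units are mmHg or beats/min. The formula applies to an ECG interval in its own units, but there is no basis in the documents for a range of S there.

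**4. Size in the individual.** Dilution by p applies only to the mean. A sedated subject's own 24-hour change contains all of S, and it is the individual change that feeds listings and any clinically-significant-change table.

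**The case against.** The case for leaving the plan alone has several parts, and most of them limit the point rather than remove it.

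- **The SAP may settle it.** Section 9.9 defers detail to the SAP, and two pre-dose series in a conditional subgroup is typical SAP material. This stands as a reason to put the repair there. The protocol rule is nevertheless unqualified, and nothing supplied overrides it.
- **It may affect almost nobody.** Subjects are aged 9 to 17, the echo procedure takes about 15 to 30 minutes (section 5.3), and sedation is only a contingency for children who cannot cooperate. This stands: the pooled effect may be near zero.
- **The consequence is limited.** Safety is a secondary objective, summarised descriptively with no hypothesis test. Section 9.5 does not expressly promise a 24-hour change-from-baseline table, and section 5.2 reports 80% to 90% of the dose eliminated by 11 minutes in adults, so the early readings matter most. This stands and lowers the severity.
- **Other provisions help.** Sedation drugs are recorded as such, investigators judge whether an adverse event is due to sedation or the product, and worsening is assessed clinically from pre dose (sections 8.4 and 8.6). These protect adverse-event reporting. They do not alter a tabulated change.
- **The pre-sedation value is not clean either.** A child who needs sedation may be distressed beforehand. This stands, and it is why simply swapping one baseline for the other is not recommended.

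Two stronger readings are tempting. A reader might infer that the pre-sedation series was intended as the 24-hour reference and then overlooked. The documents give it no such purpose; section 7.4.4.7 presents it as the start of sedation monitoring. A reader might also infer that every sedated subject's 24-hour change is in error by a known amount. The documents give no effect size, and neither pre-dose reading is established as the true resting level.

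**Conclusion.** The point holds as a minor one. As written, section 9.9 makes the post-sedation series the baseline at all time points for any sedated subject. That is suitable at 5 and 30 minutes, but it confounds the 24-hour vital-sign and ECG changes with recovery from sedation.

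Under assumed shifts of 5 to 20 units and 2% to 20% of subjects sedated, the pooled mean 24-hour change moves by about 0.1 to 4 units, and by nothing if no one is sedated. Individual listings and clinically-significant-change tables carry the whole shift for each sedated subject. The conclusion rests on recovery being complete by 24 hours, which is a reasonable inference and not a statement in the documents. The sedation rate and the size and direction of the shift are likewise assumptions. The primary efficacy endpoints and the sample size are untouched.

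**What to change.** In section 9.9, or in the SAP before database lock:

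1. Keep the last pre-dose value as baseline for the 5- and 30-minute readings in all subjects.
2. For subjects who received sedation, report the 24-hour vital-sign and ECG changes twice: from the pre-sedation series and from the post-sedation series.
3. Flag these subjects in listings and in any clinically-significant-change table.
4. Show the 24-hour summary with and without them.

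The cost is one derivation rule, a few extra table rows and a footnote. Both series and the sedation record are already on the CRF, so no data or procedures are added. The drawback is that the pre-sedation value may itself be raised by distress. Showing both changes makes that visible instead of exchanging one distortion for another.
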